6.1 General

This study is a pragmatic, prospective RCT with two arms (30). As *alivis* already holds a CE-marking, this trial will be a post-market clinical follow-up study in line with the existing intended purpose. The trial will include a control group which receives TAU ~~in addition to publicly available information material on BPD (Links to <https://borderline-info.de/> and <https://www.borderline-netzwerk.info/>),~~ and an intervention group which receives *alivis* in addition to TAU. The effectiveness of *alivis* will be tested by comparing the effects between both groups at three months (T1; primary hypothesis). Although participants will have access to *alivis* for 12 months in total, the relevant content of the intervention should be already covered after three months, with the remaining time mainly serving as refreshers and for stabilization (27). Therefore, we already expect effects to be present after three months.

Recruitment of patients will be conducted via online advertisement (e.g., Google Ads campaigns). Participants will be routed to a linked study website providing information about the trial and details about participation. Using a contact form on the website, participants will be able to indicate interest in participation whereupon they will receive an email with a link to LimeSurvey, a secure online survey tool. At the beginning of the survey, further information about participation will be provided and electronic informed consent will be obtained. Participants will be informed about the option to receive personal explanation and answers to further questions via telephone or email. Moreover, participants will be informed of their right to withdraw from the study at any time without negative consequences.

After electronic informed consent, participants will be asked to fill out an online demographic questionnaire followed by the set of questionnaires to collect baseline data (T0; see section 6.1.d) for further details). A likely diagnosis of BPD will be determined via the Borderline Symptom List-23 (BSL-23). Participants reaching a cut-off of ≥ 1.07 will be invited to a telephone interview which will serve to secure the diagnosis of BPD (via SCID-5-PD) and assess psychiatric comorbidities, rule out any comorbid diagnosis of substance use disorder or psychotic disorder, as well as an acute decompensation of mental health symptoms (via Mini-DIPS). Note that substance use and psychotic disorders were merely determined as exclusion criteria in face of the risk of non-adherence to complete questionnaires, but are not considered contraindications for the usage of *alivis*. In addition, consent to the emergency plan for suicidal crises will be obtained. This emergency plan requires that participants contact their physician/psychotherapist or the local emergency number in case of a suicidal crisis. The plan is established collaboratively with the participant at the end of the telephone interview. If inclusion and exclusion criteria are met, participants will be allocated to one of the two study groups by a computerized randomization procedure (for details, see section 6.1 b). Participants allocated to the intervention group will receive registration information for *alivis*, patients allocated to the control group will be notified ~~receive publicly available information material on BPD (Links to <https://borderline-info.de/> and <https://www.borderline-netzwerk.info/>)~~ and the information that they will receive access to *alivis* in twelve months, if they wish. All of the following measurements are carried out exclusively via online questionnaires. After three months (T1; primary timepoint for evaluation of effectiveness) participants of both groups will be asked to

complete an online questionnaire. Although participants receive access to *alivis* for 12 months, we expect highest usage of the intervention during the first months, as was the case for our intervention *priovi* (27; as well as still unpublished data from a follow-up RCT). Effects of *alivis* should therefore already be seen after three months. Additionally, patients will be surveyed after six and 12 months (T2 and T3; evaluating stability of effects). As an incentive, participants will receive a 10€ voucher from www.wunschgutschein.de per assessment (T1, T2, and T3; maximum $3 \times 10\text{€} = 30\text{€}$). All participants (from the intervention and control group) will receive this compensation if they complete the questionnaires and interview, and, in particular, the compensation in the intervention group will not depend on the actual use of *alivis*.

Contact to the participants will be established by a study director. Technical and content support for the intervention is offered via a central hotline, which is managed by a staff member who is not involved in the evaluation of the study. Participants in the intervention group will be contacted by email and/or phone if they have not redeemed their voucher for access to *alivis* 7 days after randomization. For a flow chart of the trial design, see Figure 1.

The present RCT is designed to compare *alivis* in addition to TAU with TAU only. The required initial interview to confirm diagnosis of BPD maximizes the probability that *alivis* will be tested in the appropriate intended target group.

[figure not shown]

Figure 1| Flow Chart of Trial Design

The primary time point for analysis of effectiveness of the intervention will be three months after inclusion (T1). Other timepoints of data acquisition: T2 (Follow-up) = six months after inclusion, T3 (Follow-up) = 12 months after inclusion.

a) Description of the design type of clinical investigation to be performed

- prospective
- randomized (simple randomization, 1:1, in variable blocks of 4, 8, or 16 participants each)
- two arms
- controlled (against TAU)

- online (no traditional investigation site)

b) Measures against bias

After successful screening of inclusion and exclusion criteria participants will automatically be randomized to one of two study groups (control group or intervention group) based on an algorithm.

c) Primary and secondary endpoints

Primary Endpoint: Severity of borderline symptoms at T1, assessed via the Borderline Symptoms List 23 (BSL-23).

The BSL-23 is a 23-item PROM with good psychometric properties that was validated and tested for reliability in a representative German sample (test-retest reliability $r = .82$, $p < 0.0001$; $\alpha = 0.94-0.97$; high correlation of total score with general psychological burden and depression (53)) to assess the typical symptomatology and severity of BPD (54). It refers to the last week and has a range from 0 = “not at all” to 4 = “very strong”. Its single factor structure was optimized to reflect levels and changes in severity of BPD-symptomatology based on a mean score (32).

Responders will be defined by a change of borderline symptom severity on the BSL-23 total score following both conditions: (i) reaching the cut-off of 15% of the range of the scale, i.e. improvement of 0.6 points and (ii) a change of BSL-23-total score towards a less severe grade from T0 to T1. Deteriorators will be defined accordingly by both, (i) reaching a deterioration of 0.6 points and (ii) a change of BSL-23-total score towards a more severe grade from T0 to T1. Non-responders will be defined as no change of the borderline severity grade, even if a change of 0.6 points was observed.

~~The BSL-23 is a BPD-specific PROM with good psychometric properties that was optimized to reflect levels and changes in severity of BPD-symptomatology based on a mean score (31,32).~~

~~In addition to statistical significance determined by ANCOVA, which serves as the primary analysis (see section 7), a responder analysis will be performed to assess the clinical relevance of effects of *alivis* on the severity of BPD symptoms. Responders will be defined by a change of borderline symptom severity on the BSL-23 total score following both conditions: (i) reaching the psychometric criterion of a reliable change index (RCI) (33) and (ii) a change of BSL-23 total score towards a less severe grade from T0 to T1. Deteriorators will be defined accordingly by both, (i) reaching RCI and (ii) a change of BSL-23 total score towards a more severe grade from T0 to T1.~~

~~Non responders will be defined as no change of the borderline severity grade, even if the RCI was reached.~~

Secondary Endpoints (note that the secondary endpoints are listed in priority order for the planned gatekeeping testing strategy, cf. 7.k):

Depression at T1, assessed via the Patient Health Questionnaire (PHQ-9)

The PHQ-9 is the 9-item depression module from the full PHQ with comparable sensitivity and specificity, and includes the 9 criteria upon which the diagnosis of DSM-IV depressive disorders is based. Rating will be done on a 4-point Likert scale ranging 0 = “not at all” to 3 = “nearly every day”. As a severity measure, scores range from 0 to 27 and represent: mild (<5), moderate (5-9), moderately severe (10-14), and severe depression (≥15). As a diagnostic instrument, major depression is diagnosed if 5 or more of the 9 depressive symptom criteria have been present at least “more than half the days” in the past 2 weeks, and 1 of the symptoms is depressed mood or anhedonia. “Other” depression is diagnosed if 2, 3, or 4 depressive symptoms have been present at least “more than half the days” in the past 2 weeks, and 1 of the symptoms is depressed mood or anhedonia (55). According to several studies, the German version can be considered reliable regarding psychometric standards (34–36). A reduction of 5 points will be considered as MCID (34). Responders will be defined as participants reaching this difference from T0 to T1. The proportion of responders between groups will be compared using χ^2 tests.

~~The PHQ-9 is a well-established and validated PROM in German language (34–36), to assess the 9 criteria upon which the diagnosis of DSM-IV depressive disorders is based.~~

~~A reduction of 5 points will be considered as minimal clinically important difference (MCID) (34). Responders will be defined as participants reaching this difference from T0 to T1. The proportion of responders between groups will be compared using χ^2 tests.~~

Anxiety at T1, assessed via the Generalized Anxiety Disorder Assessment (GAD-7)

This self-administered patient questionnaire is used as a screening tool and severity measure for generalized anxiety disorder (GAD) (37). Studies report good reliability, as well as criterion, construct, factorial, and procedural validity

(38,39). The GAD-7 is scored on a Likert scale ranging from 0 = “not at all” via 1 = “several days” and 2 = “more than half the days” to 3 = “nearly every day”, yielding a sum score ranging from 0-21. Scores of 5, 10, and 15 are taken as the cut-off points for mild, moderate and severe anxiety, respectively. When used as a screening tool, further evaluation is recommended when the score is 10 or greater.

~~The GAD-7 is a self-administered patient questionnaire used as a screening tool and severity measure for generalized anxiety disorder (GAD) (37). Studies report good reliability, as well as criterion, construct, factorial, and procedural validity (38,39).~~

Costs caused due to the patient's BPD

Costs caused due to BPD will be assessed with a self-compiled instrument assessing inpatient and outpatient treatment, support from friends, family and professional services, contacts with members of the judicial authorities and public security, medication, sick leave, and physician/therapist visits during work time.

Social Functioning at T1, assessed via the Work and Social Adjustment Scale (WSAS).

The WSAS is a 5-item self-report scale to measure social functioning in regard to physical, mental and social health as well as age group referenced competence for performance. The PROM has good psychometric properties with good criterion validity, good sensitivity and strong internal consistency ($\alpha = 0.89$) (40). Individual items address work, home management, social leisure, private leisure and relationships. Each item is rated on a 9-point Likert scale from 0 = “not at all impaired” to 8 = “very severely impaired”. The total score has a range of 0-40, with lower scores denoting less disability.

~~The WSAS is a scale to measure social functioning in regard to physical, mental, and social health as well as age group referenced competence for performance. The PROM is validated for a representative German sample (40).~~

Health-Related Quality of Life at T1, assessed via the AQoL-8D score on the Assessment of Quality of Life-8 Dimensions (AQoL-8D), German version

The AQoL-8D is a health-related quality-of-life questionnaire consisting of 35 items forming eight health dimensions:

independent living, happiness, mental health, coping, relationships, self worth, pain, senses. Validation of the AQoL-8D assessing health-related quality of life showed good psychometric properties in a German patient sample, including excellent reliability (Cronbach's $\alpha = 0.96$) and construct validity (strong correlation with the SF-36, $r = .81$) (41).

~~The AQoL-8D is a self-administered questionnaire to measure quality of life in 8 dimensions (independent living, happiness, mental health, coping, relationships, self worth, pain, senses) which has demonstrated good psychometric properties in a German sample (41).~~

~~Severity of borderline symptoms at T1, assessed via the Borderline Personality Disorder Checklist (BPD-CL).~~

~~The BPD-CL is a DSM-IV based self-report instrument to assess BPD symptoms in the previous month (42). Importantly, in contrast to the BSL-23, the BPD-CL explicitly assesses all nine DSM-5 criteria.~~

Patient activation at T1, assessed via the Patient Activation Measure (PAM-13)

The PAM13 assesses patients' active participation in their medical care using 13 items (43,44). Items are answered using a Likert scale ranging from 1 = "strongly disagree" to 4 = "agree strongly", yielding a total score between 13 and 52. The German version of the PAM13, the PAM13-G, is validated and demonstrates good psychometric properties, including a good internal consistency of Cronbach's $\alpha = 0.84$ (44). An improvement of 4 points on the PAM-13 is considered an MCID (56). Therefore, responders will be defined as patients who improve by at least 4 points on the PAM-13 from T0 to T2. The proportion of responders between groups will be compared using χ^2 tests.

~~The PAM-13 is a 13-item instrument assessing patients' active participation in their medical care (43). The German version of the PAM-13, the PAM-13-G, is validated and demonstrates good psychometric properties (44).~~

Exploratory Endpoints: Assessments listed in "Secondary endpoints" at T2/T3

Sociodemographic Variables:

- Age
- Gender

- Sex
- Education
- Employment Status
- Family Situation
- Language ability
- Ethnicity

Clinical Variables:

Assessed at T0 only:

- First diagnosis (date)
- Inclusion diagnosis (BPD) using the respective section of the SCID-5-PD interview (45)
- Psychiatric comorbidities (via Mini-DIPS) (46)
- Psychotherapy (past, type)

Assessed at all timepoints (T0-T3):

- Medications (name of medication, dose, frequency)
- Psychotherapy (current, type)
- Childhood trauma (via Childhood Trauma Questionnaire (CTQ; 47,48))
- Number of BPD-related hospitalizations (T0: past 12 months, T1-T2: past 3 months, T3: past 6 months)
- Number of hospitalizations due to other reasons (T0: past 12 months, T1-T2: past 3 months, T3: past 6 months)
- Number of days in sick leave (past 3 months)
- Number of days in sick pay (past 3 months)
- weight and height (current)
- Use of any other online program for BPD (T0: lifetime, T1-T2: past 3 months, T3: past 6 months; name)

Treatment satisfaction:

- Program Evaluation of the Program (NPS, Net Promoter Score) (49)
- Questionnaire on treatment satisfaction (ZUF-8; 50)
- subjective improvement of BPD symptoms and quality of life

Exploratory Variables:

- Modified version of Working Alliance Inventory WAI-I (51)

Usage monitoring (It should be noted that these data reflect only measurable engagement with *alivis* itself and do not capture how long a person has engaged with its content outside *alivis*, e.g. short text messages sent by *alivis* or PDF-materials printed from *alivis*):

- Number of chats completed
- Number of days active
- Time spent in the program

Safety and usage monitoring:

- Negative Effects Questionnaire (NEQ; (52))
- Respective user feedback via email, telephone or contact form on the *alivis* trial website
- Suicide attempts (T0-T2: past 3 months, T3: past 6 months; main safety outcome)
- other life-threatening events (e.g., non-suicidal self-injury, drug intoxication, accidents)
- Unplanned and emergency outpatient and inpatient treatments (T0-T2: past 3 months, T3: past 6 months)
- Monitoring of adverse events throughout the trial (serious adverse events will be reviewed by a Safety Officer/ PRRC)
- Usage

d) Methods and timing

Severity of Borderline Symptoms

~~The total score of the Borderline Symptoms List 23 (BSL 23)~~

~~The BSL 23 is a 23-item PROM with good psychometric properties that was validated and tested for reliability in a representative German sample (test-retest reliability $r = .82$, $p < 0.0001$; $\alpha = 0.94-0.97$; high correlation of total score with general psychological burden and depression (53)) to assess the typical symptomatology and severity of BPD (54). It refers to the last week and has a range from 0 = “not at all” to 4 = “very strong”. Its single factor structure was optimized to reflect levels and changes in severity of BPD-symptomatology based on a mean score (32).~~

~~Responders will be defined by a change of borderline symptom severity on the BSL 23 total score following both conditions: (i) reaching the psychometric criterion of a reliable change index (RCI) (33) and (ii) a change of BSL-23 total score towards a less severe grade from T0 to T1. Deteriorators will be defined accordingly by both, (i) reaching RCI and (ii) a change of BSL 23 total score towards a more severe grade from T0 to T1. Non-responders will be defined as no change of the borderline severity grade, even if the RCI was reached.~~

Depression

~~Total score of Patient Health Questionnaire (PHQ 9)~~

~~The PHQ 9 is the 9-item depression module from the full PHQ with comparable sensitivity and specificity, and includes the 9 criteria upon which the diagnosis of DSM-IV depressive disorders is based. Rating will be done on a 4-point Likert scale ranging 0 = “not at all” to 3 = “nearly every day”. As a severity measure, scores range from 0 to 27 and represent: mild (<5), moderate (5-9), moderately severe (10-14), and severe depression (≥ 15). As a diagnostic instrument, major depression is diagnosed if 5 or more of the 9 depressive symptom criteria have been present at least “more than half the days” in the past 2 weeks, and 1 of the~~

~~symptoms is depressed mood or anhedonia. “Other” depression is diagnosed if 2, 3, or 4 depressive symptoms have been present at least “more than half the days” in the past 2 weeks, and 1 of the symptoms is depressed mood or anhedonia (55). According to several studies, the German version can be considered reliable regarding psychometric standards (34–36). A reduction of 5 points will be considered as MCID (34). Responders will be defined as participants reaching this difference from T0 to T1. The proportion of responders between groups will be compared using χ^2 tests.~~

Anxiety

~~Total score of Generalized Anxiety Disorder Assessment (GAD-7)~~

~~This self-administered patient questionnaire is used as a screening tool and severity measure for generalized anxiety disorder (GAD) (37). Studies report good reliability, as well as criterion, construct, factorial, and procedural validity (38,39). The GAD-7 is scored on a Likert scale ranging from 0 = “not at all” via 1 = “several days” and 2 = “more than half the days” to 3 = “nearly every day”, yielding a sum score ranging from 0–21. Scores of 5, 10, and 15 are taken as the cut-off points for mild, moderate and severe anxiety, respectively. When used as a screening tool, further evaluation is recommended when the score is 10 or greater.~~

Costs caused due to the patient's BPD

~~Assessed with self-compiled questionnaire~~

~~Costs caused due to BPD will be assessed with a self-compiled instrument assessing inpatient and outpatient treatment, support from friends, family and professional services, contacts with members of the judicial authorities and public security, medication, sick leave, and physician/therapist visits during work time.~~

Social Functioning

~~Total score of Work and Social Adjustment Scale (WSAS) – German version~~

~~The WSAS is a 5-item self-report scale to measure social functioning in regard to physical, mental and social health as well as age group referenced competence for performance. The PROM has good psychometric properties with good criterion validity, good sensitivity and strong internal consistency ($\alpha = 0.89$) (40). Individual items address work, home management, social leisure, private leisure and relationships. Each item is rated on a 9-point Likert scale from 0 = “not at all impaired” to 8 = “very severely impaired”. The total score has a range of 0–40, with lower scores denoting less disability.~~

Health-Related Quality of Life

~~Total score of the AQoL-8D – German version~~

~~The AQoL-8D is a health-related quality of life questionnaire consisting of 35 items forming eight health dimensions: independent living, happiness, mental health, coping, relationships, self worth, pain, senses. Validation of the AQoL-8D assessing health-related quality of life showed good psychometric properties in a German patient sample, including excellent reliability (Cronbach's $\alpha = 0.96$) and construct validity (strong correlation with the SF-36, $r = .81$) (41).~~

Severity of Borderline Symptoms**Total score of the Borderline Personality Disorder Checklist (BPD-CL)**

The BPD-CL is a DSM-IV/5 based self-report instrument to assess BPD symptoms in the previous month (42). It consists of 47 items that can be grouped according to the DSM-IV/5 criteria and that are rated on a 5-point Likert scale from 1 ("not at all") to 5 ("extremely"). The original Dutch version of the BPD-CL has been validated in BPD patients and shows very good psychometric properties (Cronbach's $\alpha = 0.92$). A validation of the German version is currently in press.

Patient Activation**Total score of the Patient Activation Measure (PAM-13)**

The PAM13 assesses patients' active participation in their medical care using 13 items (43,44). Items are answered using a Likert scale ranging from 1 = "strongly disagree" to 4 = "agree strongly", yielding a total score between 13 and 52. The German version of the PAM13, the PAM13-G, is validated and demonstrates good psychometric properties, including a good internal consistency of Cronbach's $\alpha = 0.84$ (44). An improvement of 4 points on the PAM-13 is considered an MCID (56). Therefore, responders will be defined as patients who improve by at least 4 points on the PAM-13 from T0 to T2. The proportion of responders between groups will be compared using χ^2 tests.

Table 1| Chronological Sequence of the Trial

	Recruitment	Allocation	Post Allocation	Follow-up
Timepoint	T0		T1	T2, T3
Screening				
Test of Inclusion Criteria	x			
Test of Exclusion Criteria	x			
Sociodemographic Variables	x			
Clinical Variables	x		x	x
Consent	x			
Randomization		x		
Intervention				
Intervention group: alivis + TAU		♦	♦	♦
Control group: TAU + publicly available information material on BPD				
Endpoints				
BPD symptom severity (BSL-23)	x		x	x
Depression (PHQ-9)	x		x	x
General Anxiety (GAD-7)	x		x	x
Costs questionnaire	x		x	x
Social Functioning (WSAS)	x		x	x

Health-Related Quality of life (AQoL-8D)	x	x	x
BPD symptom severity (BPD-GL)	*	*	*
Patient activation (PAM-13)	x	x	x
Clinical Course	x	x	x
Net Promoter Score (NPS)*		x	x
Subjective improvement		x	x
Usage of the Program*		x	x
Exploratory Variables	x	x	x
Adverse Events (incl. NEQ)		x	x

T0: Before start of Intervention (baseline), T1: 3 months post allocation, Follow-up: T2: 6 months post allocation, T3 = 12 months post allocation. Black diamonds indicate access to *alivis*. *only assessed in the intervention group.

The primary time point for collecting data on the effectiveness of the intervention will be 3 months post allocation (T1). Six months post allocation (T2) and 12 months post allocation (T3) will be other time points for data collection, which will be treated as follow-ups to test the stability of effects. A first analysis is planned after the last patient completes T1. The complete data set will be open for analysis after the last patient completes T3. Participants will receive a 10€ voucher from www.wunschgutschein.de as an incentive for participating in T1, T2 and T3 each (max. 30€). All participants (from the intervention and control group) will receive this compensation if they complete the follow-up questionnaires, and, in particular, the compensation in the intervention group will not depend on the actual use of *alivis*. Details of data collection and analysis are summarized in Figure 1 and Table 1. The expected total duration of the study for each participant is 14 months (1 month pre-assessment, 12 months intervention phase, up to 1 month reminders for the last assessment). The expected total duration of the entire study including recruitment is estimated at 24 months.

e) Equipment for assessing the clinical investigation variables

Equipment is limited to online surveys of participants using a German provider for surveys including clinical trials, LimeSurvey. PROMs are listed under 6.1 c-d.

f) Replacement of subjects

Not applicable.

g) Investigation sites

The study is designed as an online trial; there will be no traditional physical investigation site(s). See 1.4 b and 6.1 e.

h) Completion of the clinical investigation

Data acquisition of the trial will be completed 12 to 13 months after the last patient in (up to one month buffer for reminders to complete T3). Complete analyses of the dataset will denote completion of the investigation.

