Moreover, responder analyses will be conducted. Unless a specific MCID is specified for an endpoint in section 6.1d), responders will be defined by reaching the cut-off of 15% of the range of the scale (64). ~~the reliable change index (RCI; 33) will be used to identify responders to treatment in patients with complete observations. The RCI is calculated as the ratio of the difference between pre- and post-scores of an individual participant (numerator) and the standard error of measurement of the difference (denominator). RCI scores larger than 1.96 indicate that it is unlikely that the posttest score is not reflecting real change ($p < .05$), thus indicating that the participant is a responder (33).~~ If a specific MCID is specified for an endpoint, responder analyses will instead be based on that value. Responders will then be defined as participants reaching this difference from T0 to T1. Additionally, exploratory responder analyses will be conducted for each endpoint, where response is defined as 50% improvement since baseline. The proportion of responders between groups will be compared using χ^2 tests. Moreover, the odds ratio will be reported.

d) Significance level and power

significance level (α) = 0.05 (two-sided)
power = 0.80

e) Sample size

1) Clinical data on outcome variable and effect size

An effect of Cohen's $d = 0.27$ has been observed for a digital intervention for BPD that is based on ST only (27). Given that *alivis* consists of a combination of DBT, ST, ACT, and MSC and that participants will be closely guided during the trial, we expect the observed effect to be slightly larger and assume an effect size of $d = 0.30$. In order to obtain a power of 0.80, at a two-sided significance level of 0.05, each group should have a sample size of 176. Outpatient RCTs for BPD have an average dropout rate of approximately 25% (28,29). To compensate for dropouts, we thus aim to include and randomize $N = 470$ (2×235) participants with an allocation ratio of 1:1.

2) Expected outcomes across treatment groups

See 5. d.

3) Adjustments due to pre-planned interim analyses

An interim analysis is planned after three months (T1; primary time point). There will be no adjustments.

4) Effect size and non-inferiority margin

See 7. e 1).

5) Randomization allocation ratio

1:1, in variable blocks of 4, 8, or 16 participants each ~~no block randomization, no stratification~~

6) Expected drop-out rate

25% (28,29).

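### The supplementary responder rules are inconsistent: PAM-13 response is read at T2 for a T1 endpoint, and BSL-23 response has two definitions and incomplete categories

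*Combined protocol and SAP*

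**What the plan says.** **BSL-23, section 6.1.c.** Two conditions must both hold for response. The first sets the size of the change: "i) reaching the cut-off of 15% of the range of the scale, i.e. improvement of 0.6 points". The second concerns the severity class: "ii) a change of BSL-23-total score towards a less severe grade from T0 to T1". Deterioration mirrors this, with 0.6 points of worsening and a more severe grade. The third category is set separately: "Non-responders will be defined as no change of the borderline severity grade, even if a change of 0.6 points was observed". The grades and their limits are not listed; a severity classification is cited only.

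**General rule, section 7.c.** Unless an MCID is specified for the endpoint, "responders will be defined by reaching the cut-off of 15% of the range of the scale (64". No grade condition is attached. Where an MCID is specified, "Responders will then be defined as participants reaching this difference from T0 to T1". A further exploratory analysis covers every endpoint, "where response is defined as 50% improvement since baseline". Responder proportions are compared by χ² tests, with an odds ratio.

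**PAM-13, section 6.1.c.** The endpoint is patient activation at T1 and the MCID is 4 points, but "responders will be defined as patients who improve by at least 4 points on the PAM-13 from T0 to T2". The PHQ-9 responder in the same section is read from T0 to T1, and secondary measures at T2 and T3 are classed as exploratory.

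**The concern.** Two analysts following different sections could report different BSL-23 responder rates, and the choice could be made after the data are seen. For PAM-13, the only responder definition given belongs to a timepoint that the plan treats as exploratory. It is also not fully observed when the first analysis is due, after the last patient completes T1 (sections 6.1.d and 7.h). The BSL-23 categories cannot be tabulated to add up to all patients. This matters a little more because 7.c analyses binary outcomes on non-responder imputed data and 25% dropout is expected: the category into which missing patients are placed should be properly defined. The 50% rule, applied as written, sets some patients a target that they cannot reach.

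**Working it through.** **1. The plan's threshold.** The BSL-23 mean score runs from 0 to 4 (6.1.c). 0.15 × (4 − 0) = 0.6, so the stated figure reproduces. Sections 6.1.c and 7.c therefore agree on the points and differ only on the grade condition.

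**2. BSL-23 outcomes under each section.**

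| Change T0 to T1 | Grade | 6.1.c | 7.c default |
|---|---|---|---|
| Improves ≥ 0.6 | less severe | responder | responder |
| Improves ≥ 0.6 | same | non-responder | responder |
| Improves < 0.6 | less severe | no category | not a responder |
| Worsens < 0.6 | more severe | no category | not a responder |
| Worsens ≥ 0.6 | more severe | deteriorator | not a responder |
| Worsens ≥ 0.6 | same | non-responder | not a responder |
| Any change < 0.6 | same | non-responder | not a responder |

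The second row is the conflict. It can occur only if some grade spans at least 0.6 points. The MCID exception in 7.c does not settle it: 6.1.c names no MCID for BSL-23, and the exception points to 6.1.d, where the BSL-23 text is struck out.

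The third and fourth rows are the gap. For any grade limit c, a move from c + 0.1 to c − 0.1 changes the grade by 0.2 points, which is below 0.6. The gap therefore exists for any scheme with two or more grades.

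**3. Top grade.** A patient who starts in the top grade has no worse grade to enter and cannot be a deteriorator. A worsening of 0.6 is possible on this scale only from a baseline of 4 − 0.6 = 3.4 or below. The rule therefore removes deteriorators only between the top-grade limit and 3.4. The limit is not given, so as an assumption take equal bands counted upward from the entry cut-off of 1.07:
- width 0.6: top grade starts at 1.07 + 4 × 0.6 = 3.47, above 3.4, so nothing is blocked;
- width 0.8: 1.07 + 3 × 0.8 = 3.47, again nothing is blocked;
- width 1.0: 1.07 + 2 × 1.0 = 3.07, so baselines from 3.07 to 3.4 are affected.

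**4. PAM-13.** Endpoint: T1 (3 months). Responder in 6.1.c: T0 to T2 (6 months). MCID responder in 7.c: T0 to T1. The second and third statements cannot both govern the same analysis, and the second does not match the endpoint.

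**5. The 50% rule.** PAM-13 totals run from 13 to 52, and higher is better. A 50% improvement requires T1 ≥ 1.5 × T0, hence T0 ≤ 52 / 1.5 = 34.67. From T0 = 35 the target is 52.5, which is above the maximum. For costs, the relative change (T0 − T1) / T0 has a zero denominator when baseline costs are zero.

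**The case against.** The responder analyses are supplementary. The primary test is the ANCOVA, and nothing here touches it. The sentence in 6.1.c that tied the responder analysis to clinical relevance is struck out, so a reader who infers that this is the plan's stated evidence of clinical relevance goes beyond the current text. That stands.

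The χ² test compares the proportion of responders. If everyone else stays in the denominator, a patient without a category simply counts as not a responder, and neither the rate nor the test changes. That also stands: the gap affects the non-responder count and the three-way table, not the responder comparison.

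The grade condition is deliberate, since 6.1.c says explicitly that 0.6 points without a grade change is not a response. Dropping it would be a preference, not a correction. One may add that the specific rule in 6.1.c should prevail over a general default. This is a sensible reading, but 7.c does not say so, and its only exception is for an MCID.

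A reader might infer from the top-grade point that harm is materially under-counted in the most severely ill patients. The documents do not support this. The effect depends on an unstated grade limit and may be nil. Safety rests on suicide attempts (the main safety outcome), the NEQ, emergency treatment and adverse events, and no test of deteriorators is specified.

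The 50% analysis is labelled exploratory. That lowers its importance but does not make it computable for every endpoint.

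**Conclusion.** The point holds as a set of inconsistencies in supplementary analyses, worth correcting before unblinding. Two are direct conflicts in current text: the PAM-13 response timepoint, and the BSL-23 rule in 6.1.c against the default in 7.c. Two are gaps: BSL-23 categories that do not cover all patients, and a 50% rule that fails on PAM-13 from a baseline of 35 and for zero baseline costs.

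The PAM-13 conflict and the 50% limits need no assumption. The missing BSL-23 category follows for any two or more grades. The 6.1.c against 7.c difference requires a grade at least 0.6 wide, and the top-grade block requires a top grade starting below 3.4. Because the grade limits are not in the documents, no percentage of patients affected can be defended. The ANCOVA, the gatekeeping order and the sample size are unaffected.

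**What to change.** Amend 6.1.c and 7.c before unblinding:

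- **PAM-13:** define response from T0 to T1, with T2 as exploratory follow-up.
- **BSL-23 rule:** state in 7.c which single responder rule governs, for example by cross-reference to 6.1.c, and report the other as a sensitivity or descriptive result. List the grade limits.
- **BSL-23 categories:** define a non-responder as everyone who is neither responder nor deteriorator. Tabulate worsening of 0.6 or more regardless of grade, next to a table of grade shifts.
- **50% rule:** restrict it to the zero-floor symptom scales (BSL-23, PHQ-9, GAD-7, WSAS). State how a baseline of zero is handled; this cannot arise on BSL-23, where entry requires 1.07.

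The cost is wording only. Table 1 already schedules every measure at T0, T1 and follow-up, so no data collection changes, and the sponsor's grade-based definition can be kept.
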